20.0 Publications

The data and results from the clinical investigation are the sole property of the Sponsor. The Sponsor shall have the right to access and use all data and results generated during the clinical investigation. The Investigators will not use clinical investigation-related data without the written consent of the Sponsor for any purpose other than for clinical investigation completion or for generation of publication materials, as referenced in the Clinical Trial Agreement. Single-center results are not allowed to be published or presented before the multi-center results. Any proposals for publications or presentations by the investigators must be reviewed and approved by the Sponsor in a timely manner to enable Sponsor review in compliance with the Sponsor's publication policy set forth in the Clinical Trial Agreement.

The Sponsor will register this clinical investigation on www.clinicaltrials.gov, in accordance with the International Committee of Medical Journal Editors guidelines, or any other applicable guidelines. Sponsor shall be responsible for any such registration and results posting as required by the ClinicalTrials.gov website. Institution and/or Principal Investigator(s) shall not take any action to register the clinical investigation. A full report of the pre-specified outcomes,

Clinical Investigation Plan for Europe

regardless of the results, will be made public through the ClinicalTrials.gov website no later than 12 months after clinical investigation completion, as required by section 801 of the FDA Amendments Act. If this clinical investigation is terminated early, the Sponsor will make every effort to hasten the release of the pre-specified outcomes through the ClinicalTrials.gov website.

Clinical Investigation Plan for Europe

21.0 Appendix I: Abbreviations and Acronyms

Abbreviation	Definition	Abbreviation	Definition
2°	Second degree	EP	Electrophysiology
3°	Third degree	ESC	European Society of Cardiology
6MWT	Six-minute walk test	ICD	Implantable cardioverter defibrillator
ACC	American College of Cardiology	IFU	Instructions for use
ACT	Activated clotting time	INR	International normalized ratio
ADL	Activities of daily living	IRB	Independent or institutional review board
AE	Adverse event	LP	Leadless pacemaker
AHA	American Heart Association	MET	Metabolic Equivalent of Task
AV	Atrioventricular	MRI	Magnetic resonance imaging
BBB	Bifascicular bundle branch	PA	Pulmonary arterial
CAEP	Chronotropic assessment exercise protocol	PtIr	Platinum Iridium
CFR	Complication free rate	RR	Rate response
CIP	Clinical investigation plan (also referred to as clinical protocol)	RV	Right Ventricle
CRF	Case report form	SAE	Serious adverse event
CRT	Cardiac resynchronization therapy	TiN	Titanium nitride
EC	Ethics Committee	UADE	Unanticipated adverse device effect
ECG	Electrocardiogram	USADE	Unanticipated serious adverse device effect
EGM	Electrogram		

Clinical Investigation Plan for Europe

22.0 Appendix II: Definitions

Adverse Event: An adverse event (AE) is any untoward medical occurrence, unintended disease or injury, or untoward clinical signs (including abnormal laboratory findings) in subjects, users or other persons, whether or not related to the medical device under investigation.

As part of ISO14155 Section 3.2, the Adverse Event definition has the following notes:

Note 1: This definition includes events related to the medical device under investigation or the comparator.

Note 2: This definition includes events related to the procedures involved.

Note 3: For users or other persons, this definition is restricted to events related to medical devices under investigation.

Complication: A device- or procedure-related serious adverse event, including any adverse event that prevents initial implantation.

Cardiac Tamponade: Confirmed or suspected accumulation of fluid in the pericardial space.

Cardiac Perforation: An excursion of the LP through the cardiac muscle. Signs and symptoms of a perforation by LP may include radiographic evidence of excursion of the LP into the pericardial sac, abnormal echocardiography indicative of a perforation, the accumulation of fluid in the pericardium, cardiac tamponade, or subject symptoms such as chest pain and discomfort.

Device deficiency: Any inadequacy in the identity, quality, durability, reliability, safety or performance of an investigational device, including malfunction, use errors or inadequacy in information supplied by the manufacturer.

Device-malfunction: the failure of a device to meet its performance specifications or otherwise perform as intended. Performance specifications include all claims made in the labeling for the device. The intended performance of a device refers to the intended use for which the device is labeled or marketed.

Diaphragmatic/Phrenic Nerve Stimulation: Electrical activation of the diaphragm muscle by the device output pulse. The abrupt diaphragmatic contraction is noted clinically as hiccups associated with each pacing stimulus. The pacing stimulus may stimulate the diaphragm either directly or indirectly via the phrenic nerve.

Dislodgement: The movement of the LP from its originally implanted position resulting in elevated pacing thresholds or a decrease in sensing.

Clinical Investigation Plan for Europe

Elevated Pacing Thresholds: Pacing thresholds > 2.5 V at 0.4 ms at implant. Following lead maturation at 6-8 weeks, an increase in pacing thresholds of 1.2 V at 0.4 ms or greater between visits. This definition is intended to serve as a guideline and it is understood that individual subjects may have unique situations.

Implant procedure duration: Defined as the time from delivery catheter and LP insertion to removal.

Implant success rate: Defined as the number of subjects leaving the implant procedure with an implanted and functioning LP device, divided by the number of subjects in whom implantation is attempted.

Loss of Capture: The inability of the device's output pulse to result in depolarization and contraction of the ventricle. Causes include insufficient stimulus strength, separation of the electrode from the myocardium and placement of the stimulating electrode in contact with a non-responsive portion of the myocardium such as scar tissue. Delivery of an output pulse at a time when the myocardium is physiologically refractory is not loss of capture, since capture is not physiologically feasible.

Loss of Sensing: A condition in which the pulse generator is unable to sense intrinsic cardiac signals.

Oversensing: The detection of inappropriate electrical signals by the pulse generator's sense amplifier. These signals, such as myopotentials, electromagnetic interference, or T waves must be of sufficient duration to interfere with normal device function.

Procedure duration: Defined as the time from femoral introducer insertion to removal.

Serious Adverse Event (SAE): Any untoward medical occurrence that:

- a. Led to death,
- b. Led to serious deterioration in the health of the subject, that either resulted in
 1. A life-threatening illness or injury, or
 2. A permanent impairment of a body structure or a body function, or
 3. In-patient or prolonged hospitalization, or
 4. Medical or surgical intervention to prevent life-threatening illness or injury or permanent impairment to a body structure or a body function, or requires an invasive strategy to remedy
 5. Chronic disease
- c. Led to fetal distress, fetal death or a congenital abnormality or birth defect.

Clinical Investigation Plan for Europe

NOTE: Planned hospitalization for a pre-existing condition, or a procedure required by the CIP, without serious deterioration in health, is not considered a serious adverse event.

Sponsor understands that the following items meet the definition of serious adverse event if they require hospitalization or prolong hospitalization, even though an invasive approach may not be necessary to resolve: AV fistula, pseudoaneurysm, blood transfusions, tricuspid valve damage, pericardial effusion, pulmonary embolus, device dislodgement, right ventricular perforation, thrombus formation on the device, ventricular arrhythmias even if not associated with an invasive strategy to remedy.

Non-invasive means such as device re-programming do not meet the criteria for medical or surgical intervention.

Time to discharge: Defined as the time from introducer sheath removal to discharge.

Unanticipated (serious) adverse device effect (UADE/USADE): Any serious adverse effect on health or safety or any life-threatening problem or death caused by, or associated with, a device, if that effect, problem, or death was not previously identified in nature, severity, or degree of incidence in the investigational plan or application (including a supplementary plan or application), or any other unanticipated serious problem associated with a device that relates to the rights, safety, or welfare of subjects. [21 CFR 812.3(s)]

Unavoidable adverse event: An unavoidable AE is defined as an adverse event related to the implant procedure that is expected to occur for a projected duration in all subjects.

Undersensing: The failure of the pulse generator to sense R-waves, causing delivery of inappropriately timed, asynchronous or competitive output pulses. Undersensing can sometimes be corrected by programming the device to a more sensitive setting, i.e., decreasing the millivolt value.

24.0 Appendix IV: Graded Exercise Test (CAEP Protocol)

The Chronotropic Assessment Exercise Protocol (CAEP)

Stage	Speed (MPH)	Speed (KPH)	Grade (%)	Time (min)	Cumulative time	METs
0	1.0	1.6	0	2	2	1.5
1	1.0	1.6	2	2	4	2.0
2	1.5	2.4	3	2	6	2.8
3	2.0	3.2	4	2	8	3.6
4	2.5	4.0	5	2/	10	4.6
5	3.0	4.8	6	2	12	5.8
6	3.5	5.6	8	2	14	7.5
7	4.0	6.4	10	2	16	9.6
8	5.0	8.0	10	2	18	12.1
9	6.0	9.7	10	2	20	14.3
10	7.0	11.3	10	2	22	16.5
11	7.0	11.3	15	2	24	19.0

Source:

Wilkoff, B. L., Corey J., "A Mathematical Model of the Cardiac Chronotropic Response to Exercise", Journal of Electrophysiology, 3(3) June 1989, pages 176-180

25.0 Appendix V: CIP Revision History

[illegible]

[illegible]

Clinical Investigation Plan for Europe

	

Clinical Investigation Plan for Europe

26.0 Appendix VI: CIP Summary (Synopsis) – Phase 2

CIP Summary (Synopsis) – Phase 2	
Title	A safety and effectiveness trial for a leadless pacemaker system – The LEADLESS II Study – Phase 2
Investigational Device	Aveir Leadless Pacemaker (LP) – Model LSP112V
Regulatory Classification of the Investigational Device	Class III
Number of Institutions	Up to 80 sites worldwide with up to 60 investigation sites in the United States. [REDACTED]
Number of Subjects	Up to 210 [REDACTED]
Trial Population	Subjects who are at least 18 years old, and who are indicated for a VVI(R) pacemaker
Schedule of Assessments	Enrollment, Implant, Pre-Discharge, 2-week, 6-week, 3-month, 6-month follow-up, 12-month follow-up, and every 6 months thereafter until study completion.
Study Design	Prospective, non-randomized, single-arm, international multicenter, clinical safety and effectiveness investigation.
Study Objective	The primary objectives of this study are to confirm the clinical safety and effectiveness of the Aveir LP system in subjects who are indicated for VVI(R) pacemaker.
Confirmatory Safety Endpoint	The confirmatory safety endpoint evaluates the 12-month complication-free rate.
Confirmatory Effectiveness Endpoint	The confirmatory effectiveness endpoint evaluates pacing thresholds and R-wave amplitudes within the therapeutic range through 12-months post-implant.
Confirmatory Secondary Endpoint	The confirmatory secondary endpoint evaluates an appropriate and proportional rate response during graded exercise testing (CAEP protocol), performed after the beginning of the 6-week visit.

Clinical Investigation Plan for Europe

CIP Summary (Synopsis) – Phase 2	
Pre-market submissions	Pre-market submissions of clinical data from this IDE study to regulatory agencies will be per local requirements.
	
Inclusion Criteria	
Eligible subjects will meet all of the following:
 
 Subject must have one of the clinical indications before device implant in adherence with ACC/AHA/HRS/ESC single chamber pacing guidelines including: 
  Chronic and/or permanent atrial fibrillation with 2 or 3° AV or bifascicular bundle branch block (BBB block), including slow ventricular rates (with or without medication) associated with atrial fibrillation; or  Normal sinus rhythm with 2 or 3° AV or BBB block and a low level of physical activity or short expected lifespan (but at least one year); or  Sinus bradycardia with infrequent pauses or unexplained syncope with EP findings; and Subject ≥ 18 years of age; and Subject has life expectancy of at least one year; and *Subject is not enrolled in another clinical investigation; and Subject is willing to comply with clinical investigation procedures and agrees to return for all required follow-up visits, tests, and exams; and Subject has been informed of the nature of the study, agrees to its provisions and has provided written informed consent, approved by the IRB/EC; and Subject is not pregnant and does not plan to get pregnant during the course of the study.
Exclusion Criteria	
Subjects will be excluded if they meet any of the following:
 
 Subject has known pacemaker syndrome, has retrograde VA conduction or suffers a drop in arterial blood pressure with the onset of ventricular pacing; or Subject is allergic or hypersensitive to <1 mg of dexamethasone sodium phosphate; or Subject has a mechanical tricuspid valve prosthesis; or Subject has a pre-existing endocardial pacing or defibrillation

Clinical Investigation Plan for Europe

CIP Summary (Synopsis) – Phase 2	
	
leads; or
 
5. Subject has current implantation of either conventional or subcutaneous implantable cardioverter defibrillator (ICD) or cardiac resynchronization therapy (CRT); or
 
6. Subject has an implanted vena cava filter; or
 
7. Subject has evidence of thrombosis in one of the veins used for access during the procedure; or
 
8. Subject had recent cardiovascular or peripheral vascular surgery within 30 days of enrolment; or
 
9. *Subject has an implanted leadless cardiac pacemaker
 
10. **Subject is implanted with an electrically-active implantable medical device with stimulation capabilities (such as neurological or cardiac stimulators).
 
* Except for subjects who are enrolled in the Leadless Observational Study and need their existing Nanostim LP replaced with the Aveir LP. These subjects may only be enrolled in this IDE during the CAP study of Phase 2.
 
** Does not apply to a medical device known to not be impacted by the Aveir™ Link Module telemetry signals or to a medical device than can be temporarily turned off during interrogation/programming of an Aveir™ LP

Enrollment	Subjects who sign an IRB/EC-approved informed consent and have an attempted implant will be considered enrolled in the study.
Schedule of Assessments	Pre-procedure Assessments 
 • Inclusion/exclusion criteria • Informed consent

Clinical Investigation Plan for Europe

CIP Summary (Synopsis) – Phase 2	
Schedule of Assessments (Cont'd)	
 • Pregnancy assessment • 12-lead ECG • Medical history • Medications⁶ 
Implant Assessments
 
 • Femoral vein assessment and access • Procedure details • LP implant • LP assessment and programming • Assess for changes in medications or change in therapy • Assess for AEs 
Post-procedure Assessments
 
 • Access-site assessment • 12-lead ECG • X-ray of pacemaker • LP assessment and programming • Assess for changes in medications or change in therapy • Assess for AEs 
2-week Visit
 
 • LP assessment and programming • Assess for changes in medications or change in therapy • Assess for AEs • Sensor parameter optimization test (6MWT) until approximately 30 subjects provide data contributing to the analysis (optional) 
6-week Visit
 
 • LP assessment and programming • Assess for changes in medications or change in therapy • Assess for AEs • Graded exercise test (CAEP protocol) until approximately 30 subjects provide data contributing to the analysis (optional) 
3-month Visit
 
 • LP assessment and programming • Assess for changes in medications or change in therapy • Assess for AEs

⁶ Data are collected for beta blocker, ACE, ARB, anti-arrhythmic, anti-coagulant, and anti-platelet medications, at all visits.

Clinical Investigation Plan for Europe

CIP Summary (Synopsis) – Phase 2	
	
• 6MWT (optional)• CAEP (optional) 
6-month Visit
 
• LP assessment and programming• Assess for changes in medications or change in therapy• Assess for AEs• 6MWT (optional)• CAEP (optional) 
12-month Visit and Every 6-month Visits thereafter
 
• LP assessment and programming• Assess for changes in medications or change in therapy• Assess for AEs• 6MWT (optional)• CAEP (optional)

Clinical Investigation Plan for Europe

27.0 Appendix VII: Continued Access Phase for European sites

1000

1997, 1998, 1999, 2000, 2001, 2002, 2003, 2004, 2005, 2006, 2007, 2008, 2009, 2010, 2011, 2012, 2013, 2014, 2015, 2016, 2017, 2018, 2019, 2020, 2021, 2022, 2023, 2024, 2025, 2026, 2027, 2028, 2029, 2030, 2031, 2032, 2033, 2034, 2035, 2036, 2037, 2038, 2039, 2040, 2041, 2042, 2043, 2044, 2045, 2046, 2047, 2048, 2049, 2050, 2051, 2052, 2053, 2054, 2055, 2056, 2057, 2058, 2059, 2060, 2061, 2062, 2063, 2064, 2065, 2066, 2067, 2068, 2069, 2070, 2071, 2072, 2073, 2074, 2075, 2076, 2077, 2078, 2079, 2080, 2081, 2082, 2083, 2084, 2085, 2086, 2087, 2088, 2089, 2090, 2091, 2092, 2093, 2094, 2095, 2096, 2097, 2098, 2099, 2100, 2101, 2102, 2103, 2104, 2105, 2106, 2107, 2108, 2109, 2110, 2111, 2112, 2113, 2114, 2115, 2116, 2117, 2118, 2119, 2120, 2121, 2122, 2123, 2124, 2125, 2126, 2127, 2128, 2129, 2130, 2131, 2132, 2133, 2134, 2135, 2136, 2137, 2138, 2139, 2140, 2141, 2142, 2143, 2144, 2145, 2146, 2147, 2148, 2149, 2150, 2151, 2152, 2153, 2154, 2155, 2156, 2157, 2158, 2159, 2160, 2161, 2162, 2163, 2164, 2165, 2166, 2167, 2168, 2169, 2170, 2171, 2172, 2173, 2174, 2175, 2176, 2177, 2178, 2179, 2180, 2181, 2182, 2183, 2184, 2185, 2186, 2187, 2188, 2189, 2190, 2191, 2192, 2193, 2194, 2195, 2196, 2197, 2198, 2199, 2200, 2201, 2202, 2203, 2204, 2205, 2206, 2207, 2208, 2209, 2210, 2211, 2212, 2213, 2214, 2215, 2216, 2217, 2218, 2219, 2220, 2221, 2222, 2223, 2224, 2225, 2226, 2227, 2228, 2229, 2230, 2231, 2232, 2233, 2234, 2235, 2236, 2237, 2238, 2239, 2240, 2241, 2242, 2243, 2244, 2245, 2246, 2247, 2248, 2249, 2250, 2251, 2252, 2253, 2254, 2255, 2256, 2257, 2258, 2259, 2260, 2261, 2262, 2263, 2264, 2265, 2266, 2267, 2268, 2269, 2270, 2271, 2272, 2273, 2274, 2275, 2276, 2277, 2278, 2279, 2280, 2281, 2282, 2283, 2284, 2285, 2286, 2287, 2288, 2289, 2290, 2291, 2292, 2293, 2294, 2295, 2296, 2297, 2298, 2299, 2300, 2301, 2302, 2303, 2304, 2305, 2306, 2307, 2308, 2309, 2310, 2311, 2312, 2313, 2314, 2315, 2316, 2317, 2318, 2319, 2320, 2321, 2322, 2323, 2324, 2325, 2326, 2327, 2328, 2329, 2330, 2331, 2332, 2333, 2334, 2335, 2336, 2337, 2338, 2339, 2340, 2341, 2342, 2343, 2344, 2345, 2346, 2347, 2348, 2349, 2350, 2351, 2352, 2353, 2354, 2355, 2356, 2357, 2358, 2359, 2360, 2361, 2362, 2363, 2364, 2365, 2366, 2367, 2368, 2369, 2370, 2371, 2372, 2373, 2374, 2375, 2376, 2377, 2378, 2379, 2380, 2381, 2382, 2383, 2384, 2385, 2386, 2387, 2388, 2389, 2390, 2391, 2392, 2393, 2394, 2395, 2396, 2397, 2398, 2399, 2400, 2401, 2402, 2403, 2404, 2405, 2406, 2407, 2408, 2409, 2410, 2411, 2412, 2413, 2414, 2415, 2416, 2417, 2418, 2419, 2420, 2421, 2422, 2423, 2424, 2425, 2426, 2427, 2428, 2429, 2430, 2431, 2432, 2433, 2434, 2435, 2436, 2437, 2438, 2439, 2440, 2441, 2442, 2443, 2444, 2445, 2446, 2447, 2448, 2449, 2450, 2451, 2452, 2453, 2454, 2455, 2456, 2457, 2458, 2459, 2460, 2461, 2462, 2463, 2464, 2465, 2466, 2467, 2468, 2469, 2470, 2471, 2472, 2473, 2474, 2475, 2476, 2477, 2478, 2479, 2480, 2481, 2482, 2483, 2484, 2485, 2486, 2487, 2488, 2489, 2490, 2491, 2492, 2493, 2494, 2495, 2496, 2497, 2498, 2499, 2500, 2501, 2502, 2503, 2504, 2505, 2506, 2507, 2508, 2509, 2510, 2511, 2512, 2513, 2514, 2515, 2516, 2517, 2518, 2519, 2520, 2521, 2522, 2523, 2524, 2525, 2526, 2527, 2528, 2529, 2530, 2531, 2532, 2533, 2534, 2535, 2536, 2537, 2538, 2539, 2540, 2541, 2542, 2543, 2544, 2545, 2546, 2547, 2548, 2549, 2550, 2551, 2552, 2553, 2554, 2555, 2556, 2557, 2558, 2559, 2560, 2561, 2562, 2563, 2564, 2565, 2566, 2567, 2568, 2569, 2570, 2571, 2572, 2573, 2574, 2575, 2576, 2577, 2578, 2579, 2580, 2581, 2582, 2583, 2584, 2585, 2586, 2587, 2588, 2589, 2590, 2591, 2592, 2593, 2594, 2595, 2596, 2597, 2598, 2599, 2600, 2601, 2602, 2603, 2604, 2605, 2606, 2607, 2608, 2609, 2610, 2611, 2612, 2613, 2614, 2615, 2616, 2617, 2618, 2619, 2620, 2621, 2622, 2623, 2624, 2625, 2626, 2627, 2628, 2629, 2630, 2631, 2632, 2633, 2634, 2635, 2636, 2637, 2638, 2639, 2640, 2641, 2642, 2643, 2644, 2645, 2646, 2647, 2648, 2649, 2650, 2651, 2652, 2653, 2654, 2655, 2656, 2657, 2658, 2659, 2660, 2661, 2662, 2663, 2664, 2665, 2666, 2667, 2668, 2669, 2670, 2671, 2672, 2673, 2674, 2675, 2676, 2677, 2678, 26

[REDACTED]

Leadless Observational Study Roll-Over Subjects

Clinical Investigation Plan for Europe

[REDACTED]

[REDACTED]

[REDACTED]

[REDACTED]

[REDACTED]

[REDACTED]	[REDACTED]
[REDACTED]	[REDACTED]
[REDACTED]	[REDACTED]
[REDACTED]	[REDACTED]
[REDACTED]	[REDACTED]
[REDACTED]	[REDACTED]
[REDACTED]	[REDACTED]
[REDACTED]	[REDACTED]
[REDACTED]	[REDACTED]
[REDACTED]	[REDACTED]
[REDACTED]	[REDACTED]
[REDACTED]	[REDACTED]
[REDACTED]	[REDACTED]

Clinical Investigation Plan for Europe

## Statistical Analysis Plan

### 1.0 **SYNOPSIS OF STUDY DESIGN**

#### 1.1 **Purpose of the Statistical Analysis Plan**

This statistical analysis plan (SAP) is intended to provide a detailed and comprehensive description of the planned methodology and analysis to be used for submission for CE Mark approval based on The LEADLESS II Study – Phase 2 (A safety and effectiveness trial for a leadless pacemaker system), the ABT-CIP-10355 (CRD-701) clinical investigation. This plan is based on the ABT-CIP-10355 Ver. C, September 24, 2021 Clinical Investigation Plan (CIP).

#### 1.2 **Clinical Investigation Objectives**

The primary objectives of Phase 2 are to confirm the safety and effectiveness of the Aveir™ Leadless Pacemaker System device from implant through 12-months in a subject population indicated for a VVI(R) pacemaker.

#### 1.3 **Clinical Investigation Design**

The Leadless II study- Phase 2 is a prospective, non-randomized, multi-center, international clinical study designed to **confirm** the safety and effectiveness of the Aveir LP System in a subject population indicated for a VVI(R) pacemaker.

Sponsor will conduct the study at up to 80 centers worldwide (

#### 1.4 **Endpoints**

The Phase 2 of the study will include the following confirmatory endpoints.

##### 1.4.1 **Confirmatory Safety Endpoint**

The confirmatory safety endpoint evaluates a 12-month complication-free rate based on CEC adjudication of adverse events.

##### 1.4.2 **Confirmatory Effectiveness Endpoint**

The confirmatory effectiveness endpoint evaluates pacing thresholds and R-wave amplitudes within the therapeutic range through 12 months post-implant.

##### 1.4.3 **Confirmatory Secondary Endpoint**

The confirmatory secondary endpoint evaluates an appropriate and proportional rate response during graded exercise testing (CAEP protocol).

## Statistical Analysis Plan

### 1.5 Randomization

Not applicable

### 1.6 Blinding

Not applicable

## 2.0 ANALYSIS CONSIDERATIONS

The summary and analysis described in this SAP will apply to CE mark submission of The Leadless II Study- Phase 2 and its clinical report(s).

### 2.1 Analysis Populations

The following analysis populations are defined for the study.

#### 2.1.1 Enrolled Population

The Enrolled population includes all subjects who are enrolled in Phase 2 of the study. Subjects who sign an IRB/EC-approved informed consent and have an attempted implant will be considered enrolled in the study.

An attempted implant is defined as the point of skin incision for the insertion of the Aveir Introducer (LSN25301 or LSN25501) for the implant procedure.

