3.2.1 Confirmatory Endpoints

3.2.1.1 Confirmatory Safety Endpoint

The goal of the confirmatory safety endpoint evaluation is to demonstrate an acceptable complication-free rate (CFR); including any complication that prevents initial implantation.

[REDACTED]

Confirmatory Safety Endpoint Evaluation at 12-months:

H_0 : CFR \leq 83% vs. H_1 : CFR $>$ 83%

[REDACTED]

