3.5.3 Implant Procedure

3.5.3.1 Femoral Vein Assessment and Access

Although sponsor supports using either technique for assessing

Clinical Investigation Plan for Europe

femoral vein access-site location, size and presence of disease, investigator will use medical judgment and follow institutional standard of care when accessing the femoral vein during catheter-based procedures.

The ideal puncture site should be located **below the inguinal ligament and above the bifurcation** (Refer to **Figure 7**).^{5,8-10} Penetrate the skin and puncture the femoral vein using the Seldinger technique. Due to the introducer sheath size, investigator may need to “nick and spread” the tissue at the access-site location to allow for easier transition of the introducer sheath through the tissue tract.

[figure not shown]

Figure 7: Location of femoral vein in relation to femoral artery, inguinal ligament and femoral head

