18.6 Case Report Form Completion

Primary data collection based on source-documented hospital and/or clinic chart reviews will be performed clearly and accurately by site personnel trained on the CIP and CRF completion. The investigator will ensure accuracy, completeness, legibility and timeliness of the data reported to the Sponsor on the CRFs and in all required reports. Data on CRFs will be collected for all subjects that are enrolled into the clinical investigation.

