#### 2.3.1 Confirmatory Safety Endpoint

The confirmatory safety endpoint evaluates the 12-month complication-free rate (CFR) based on CEC adjudication of the adverse event. Complication is defined as a device-or-procedure-related serious adverse event, including those that prevent initial implantation. This definition of complication is equivalent to the term SADE (Serious Adverse Device Effect) throughout this SAP. The CEC will make the final determination regarding whether an adverse event meets the criteria for the confirmatory endpoint analysis.

The confirmatory safety hypothesis at 12 months timepoint is:

$H_0$ : CFR  $\leq$  83% vs.  $H_1$ : CFR  $>$  83 %

where 83% is the performance goal.

[REDACTED]

[REDACTED]

SADE events that occur on or before the 12-month follow-up visit (360 days) will be included in the confirmatory safety endpoint analysis.

To eliminate the possible impact of Covid-19 on the confirmatory safety endpoint analysis, CEC adjudicated primary safety events (SADEs) that are related or possibly related to Covid-19 will be excluded from the confirmatory safety endpoint analysis. Subjects who have these events will be censored at the time of the event. Additional analysis with these events included will also be provided.

Additional sensitivity analysis based on all the enrolled subjects to assess the impact of missing data on the confirmatory safety endpoint will be performed and they are described in Section 2.8.

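### Enrolment starts at skin incision, but access is a needle puncture with an optional nick, so a serious access complication that ends the procedure before any incision drops out of the safety analysis

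*SAP*

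**What the plan says.** SAP 2.1.1 sets the enrolment rule: "Subjects who sign an IRB/EC-approved informed consent and have an attempted implant will be considered enrolled in the study". It then fixes the moment of the attempt: "An attempted implant is defined as the point of skin incision for the insertion of the Aveir Introducer". Protocol 3.5.1.1 and the synopsis in Appendix VI use the same enrolment rule. Their visible text does not define the attempt, so SAP 2.1.1 holds the only visible operational definition.

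Protocol 3.5.3.1 describes how the vein is reached: "Penetrate the skin and puncture the femoral vein using the Seldinger technique". The nick comes next in the text and is conditional: "Due to the introducer sheath size, investigator may need to" open the tissue at the access site. Its stated purpose is "to allow for easier transition of the introducer sheath through the tissue tract".

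The scope of the safety endpoint is wide. Protocol 3.2.1.1 describes the CFR as "including any complication that prevents initial implantation", and SAP 2.3.1 says: "Complication is defined as a device-or-procedure-related serious adverse event, including those that prevent initial implantation".

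**The concern.** The endpoint is meant to count a complication that stops the implant from happening. The enrolment trigger sits at a step that may come after the first invasive act, or may not occur at all. A serious complication from the needle or guidewire can therefore end the procedure before the subject qualifies for the population in which that complication would be counted. Membership of the analysis set then depends in part on the outcome.

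This touches a risk the trial is meant to measure. Protocol Table 6 lists arterial puncture, AV fistula, bladder puncture and retroperitoneal haematoma among foreseeable events. Protocol 10.1 and 10.4 name percutaneous femoral delivery as a novel feature whose risk is uncertain. A complication lost in this way can only raise the CFR that is compared with the 83% performance goal.

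**Working it through.** The plan states no figure on this point, and the sample size section (SAP 2.4) is redacted, so there is nothing to reproduce. The check has two parts: the text, then the scale.

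**Text.** Take a consented subject with a serious vessel injury from the needle, whose procedure is stopped before any nick.

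- SAP 2.1.1: no skin incision for the introducer, so no attempted implant and no enrolment.
- SAP 2.3.1: the missing-data sensitivity analysis for safety uses all enrolled subjects, so this subject is not in it.
- SAP 2.9: poolability of the safety endpoint is assessed on enrolled subjects.
- SAP 3.2: adverse event tables, including those for adjudicated events, are on all enrolled subjects.
- Protocol 3.2.1.1 and SAP 2.3.1: the event is of the kind the endpoint is meant to include.

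No visible analysis recovers this subject.

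**Scale: inputs.** N = 210 (SAP 2.3) and performance goal 83% (SAP 2.3.1). Assumed, because not visible: an exact one-sample binomial test, complete 12-month follow-up, and one-sided alpha of 0.025 or 0.05. The number k of omitted complications is also an assumption, because the documents give no rate.

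**Shift in CFR.** With c complications counted among 210, each omitted subject adds one complication and one to the denominator, so the shift is (210 − c)/210 − (210 − c)/(210 + k).

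| c | k = 1 | k = 2 | k = 5 |
|---|---|---|---|
| 10 | 200/210 − 200/211 = 95.24% − 94.79% = 0.45 points | 95.24% − 94.34% = 0.90 | 95.24% − 93.02% = 2.21 |
| 25 | 185/210 − 185/211 = 88.10% − 87.68% = 0.42 points | 88.10% − 87.26% = 0.83 | 88.10% − 86.05% = 2.05 |

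(Differences are taken before rounding.)

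**Limit for success.** Find the smallest r with P(X ≥ r) ≤ alpha, where X is binomial(210, 0.83).

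- One-sided 0.025: r = 186, p = 0.0163, so at most 210 − 186 = 24 complications.
- One-sided 0.05: r = 184, p = 0.0415, so at most 210 − 184 = 26 complications.

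**Effect at the limit.** Keep r fixed and raise N to 210 + k.

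- One-sided 0.025: 186/211 gives p = 0.0248, still a pass. 186/212 gives p = 0.0365, a fail.
- One-sided 0.05: 184/211 gives p = 0.0587, a fail.

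A normal-approximation lower bound, which equals a Kaplan-Meier bound with Greenwood's variance when nobody is censored, moves the limits to 26 and 27 complications. The exact limits therefore depend on the test, which is not visible.

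**The case against.** The strongest reply is that a sensible reader takes incision for the introducer to mean the start of access. The introducer has a 25F inner diameter, and it is a defensible design choice to tie the attempt to the first component of the investigational system. That may be what the sponsor intends. If so, the SAP should say it, because sites could otherwise apply the wording differently. The endpoint also covers procedure-related events, so needle access belongs inside it.

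The order of puncture and nick is partly inferred: Protocol 3.5.3.1 does not require the nick to follow the needle, and some text in that section is missing. Text is also redacted in the enrolment, safety endpoint and missing-data sections. A hidden rule could close the gap, but only by reaching beyond enrolled subjects, and the visible text points the other way.

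A reader might infer more than the documents support:

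- *That these events are never recorded.* Protocol 18.6 says "Data on CRFs will be collected for all subjects that are enrolled into the clinical investigation". It does not restrict collection to those subjects, and Protocol 6.0 asks the investigator to document all adverse events. What the text supports is loss from the analyses.
- *That a subject whose sheath passes without a nick is not enrolled.* This is too literal. Protocol 3.5.1.1 treats a subject who is implanted as a study subject, and SAP 2.1.2 places successful implants within enrolment.
- *That access complications in general are excluded.* Only procedures abandoned between puncture and incision are affected. An injury in a procedure that goes on to an incision is counted, as are events from the dilator, sheath or catheter after an incision.

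**Conclusion.** The point holds in a narrow form. As written, the enrolment trigger conflicts with the endpoint's own scope for one group: consented subjects whose procedure ends because of a serious needle or guidewire complication before any skin incision. Leaving out such a complication can only favour the device.

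The size is probably small, at about 0.4 to 0.5 points of CFR per omitted subject. Under the assumptions stated, the conclusion would change only if the result lay within one or two events of the limit (24 complications at one-sided 0.025, 26 at one-sided 0.05). The documents give no frequency for such events. An illustration with four omitted subjects might suggest 4/210 = 1.9 points, but those subjects also enter the denominator. The shift is then 186/210 − 186/214 = 1.66 points with 24 complications counted, or 200/210 − 200/214 = 1.78 with 10. The finding does not show that the CFR is materially biased; it shows that the definition leaves a gap with a known direction.

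**What to change.** In SAP 2.1.1, define an attempted implant as beginning at the first percutaneous puncture for venous access for the Aveir procedure. Put the identical definition in Protocol 3.5.1.1 at its next amendment.

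For any consented subject who was punctured but is not enrolled under the present definition, list the subject with all adverse events. Report a sensitivity analysis of the CFR that adds these subjects to the denominator and their complications to the complication count. Do not silently alter the confirmatory set of 210.

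The cost is modest but not nil. The CFR may fall slightly. A protocol wording change needs the approvals described in Protocol 16.0. Finding past cases depends on site records that the visible documents do not describe, and follow-up on those subjects may be short. No clinical procedure changes.
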